##### **1. Background/Rationale**

Racial and ethnic disparities in Alzheimer's disease and related dementias (ADRD) are pervasive. Major racial and ethnic inequalities in dementia incidence have been reported across cohort studies [1]. Compared to Whites and Asians, Blacks and Hispanics have a higher prevalence of dementia [2, 3]. These differences carry into disease severity and presentation [4, 5]. African American/Black and Hispanic/Latino(a) patients display a greater severity of cognitive symptoms at time of disease onset [6].

Despite this level of vulnerability to ADRD and the increasing racial and ethnic diversity of the US population [7], Hispanic/Latino individuals and non-white individuals of lower socioeconomic status and lower educational levels are minimally represented in clinical trials [8, 9]. The FDA reports that only 5% of clinical trial participants are Black, and only 1% are Latino(a) [10]. These proportions grossly underrepresent the respective distributions of these groups within the US population [7]. The concerted efforts from guiding agencies and experts have helped to prioritize the increased representation of groups with diverse demographic attributes [11, 12]. Nevertheless, barriers to recruitment of underrepresented groups into clinical trials remain [13, 14].

AD clinical trials, especially those targeting the preclinical/prodromal stage, face specific hurdles. AD trials are frequently delayed due to slow patient enrollment, long follow-up periods, higher costs, and other operational challenges compared with trials in other therapeutic areas [16]. The challenges in enrollment are further exacerbated when it comes to populations of diverse demographic backgrounds, particularly non-white individuals who have markedly higher rates of AD but lower access to and use of care than non-Hispanic Whites [17-19]. The FDA indicates that less than 6% of clinical trial participants are from these underrepresented groups. With the projected increase of AD over the next three decades among individuals who identify as being African American/Black, Hispanic/Latino(a), and Asian, increasing representation of these groups across preclinical/prodromal AD clinical trials is critical. Implementation of inclusive recruitment strategies that engage these populations is of paramount importance.

The goal of this work is to explicitly test whether financial incentives can be used to increase the diversity of participants recruited to the Alzheimer Prevention Trials (APT) Webstudy (USC IRB, HS-17-00746), an innovative online registry of adults with concerns about memory problems who are routinely assessed for eligibility and recruitment into the Trial Ready Cohort for the Prevention of Alzheimer's Disease (TRC-PAD) (Advarra IRB, Pro00030367) and ultimate enrollment into early-stage ADRD trials [15].

The APT Webstudy is a longitudinal study that serves as a web-based registry to improve the efficiency at which participants at early stages of AD can be screened. Screening within the APT Webstudy occurs

Revised 03-07-23

through quarterly remote cognitive assessments. Data is analyzed monthly using an adaptive algorithm to assess each participant's risk of AD. Participants at high risk for AD are referred for cognitive testing, genotyping, and amyloid biomarker measures at clinical trial sites to determine Trial-Ready Cohort (TRC) eligibility. Participants that are TRC eligible are enrolled and followed longitudinally until an appropriate clinical trial becomes available. Thus, the APT Webstudy is an important first step in casting a wide net to identify individuals that may not yet have concerns related to their memory and may not have sought medical attention with cognitive concerns. The convenience of remote assessment and the low burden to potential clinical trial participants make it an excellent platform to evaluate recruitment and retention practices across populations. To date, the APT Webstudy has consented over 48,000 participants. The APT Webstudy and TRC-PAD Study are overseen by USC's Alzheimer's Therapeutic Research Institute (ATRI).

While remote registries, like the APT Webstudy, offer numerous advantages such as accessibility and low burden to individuals eligible for in-person multisite trials, particularly at the recruitment level, representation from diverse groups is still limited. A well-known barrier to ethnocultural diversity is the lack of trust in the academic and medical establishments that are often involved in clinical trials [3]. Approaching issues of mistrust requires time, relationship building and resources [13, 24, 25] that are not often built into the clinical trial infrastructure. Numerous studies show that collaboration with existing trusted community partners in recruitment may be effective at increasing the enrollment of minoritized communities into research [25-27].

Financial incentives are common in behavioral change interventions including medication and exercise adherence and hypertension management [28-31]. Results from a weight loss study indicate that participants who received financial incentives were more likely to temporarily maintain weight loss than those who did not [1]. In a tobacco cessation program, African American and English-speaking Latino(a) participants were more engaged when financial incentives were included [32]. An earlier RCT aimed at smoking cessation showed that in a diverse cohort of 352 underserved adults (mean age of 50) at a large urban safety-net hospital, patient navigation and financial incentives significantly increased rates of uptake. Subgroup analyses suggested that the navigation and financial incentives were particularly beneficial in older participants, women, non-Hispanic White and lower socioeconomic status (SES) participants [33]. Although participants are commonly compensated for their enrollment in clinical trials, as well as at the assessment of primary endpoints, financial incentives have seldom been used in AD trials. Notably, lottery systems have recently been adopted to incentivize individuals to receive the COVID-19 vaccination [34]. Research into understanding which method of incentivizing AD participants is most effective from a recruitment standpoint and from a cost standpoint would be valuable for all future trials.

## 2. Purpose/Objectives/Aims/Research Questions

Primary Objectives: To assess the impact of offering financial incentives (a certain small financial incentive or a randomized prize incentive) on enrollment rates of a population of diverse low-income adults ages 50 years and older into the APT Webstudy.

Secondary Objectives: To test whether the prize incentive is more effective at increasing enrollment than the certain small financial incentive. To assess the impact of financial incentives on cost per enrollee and, separately, completion of two cognitive assessments.

Tertiary Objectives: To analyze all primary and secondary outcomes for the following subgroup characteristics at baseline: sex (M/F), race and ethnic groups (Latino/Hispanic, non-Hispanic White, non-

Hispanic Black, non-Hispanic Asian, Other), primary language (English/Spanish), message modality (email or text) and age group (50-64, 65-74, 75 and over).

### 3. Participants (sample)

#### **Inclusion Criteria:**

To be eligible to participate in this study, an individual must meet all of the following criteria:

- i. Patients empaneled at Contra Costa Regional Medical Center (CCRMC), the county public hospital and its affiliated health centers.
- ii. Age 50 or older
- iii. Literate in either English or Spanish

Inclusion criteria are justified because only those age 50 and over are eligible for the APT Webstudy and the APT Webstudy is only available in English and Spanish. Because CCRMC is a county health system, most of its patients are low income. They also are racially and ethnically diverse. These characteristics are under-represented in brain health registries and clinical trials for AD, despite increased risk of AD.

#### **Exclusion Criteria:**

Individuals who meet any of the following criteria will be excluded from participation in this study:

- I. Below age 50
- II. Documentation of prior dementia diagnosis

Exclusion criteria are justified because those below age 50 and those with dementia are ineligible for the existing APT Webstudy.

### 4. Recruitment/Screening Process (sampling strategy)

Our study partner, CCRMC, will provide the research team with an anonymous dataset that contains a unique code for all CCRMC patients who meet the inclusion and exclusion criteria for the study as well as their age in years, gender, race/ethnicity, preferred communication language (English/Spanish), preferred mode of communication from the health system (SMS or email) and insurance type. Only the health system, CCRMC, will be able to ascertain the identity of patients from these codes. The research team will not have access to the codes at any time. This anonymous dataset will be used for the purposes of randomly assigning patients to one of the three study arms: (1) message-only arm, (2) small financial incentive arm or (3) prize opportunity arm. Randomization will be stratified 1:1:1 by age group (50-64, 65 and over), race and ethnic status (Latino/Hispanic, non-Hispanic White, non-Hispanic Black, non-Hispanic Asian, Other) and message modality (email or text). The other covariates in the dataset will be used to check for balance in observable characteristics across study arm. We have worked with CCRMC on several prior projects and have an established process for collaboration.

The study team will then return the anonymous data (with a unique code only known to the health system) to CCRMC with a new study arm variable showing the assigned study arm for each of the included patients. The health system will then send SMS messages or e-mail, depending on the

member's preferred mode of communication (SMS/e-mail), inviting members to participate in the APT Webstudy and offering them an incentive (small certain or prize opportunity) if the member was assigned to one of the incentive arms. All messages will be *sent by the health system and* delivered in English or Spanish, depending on the preferred language. Within two weeks of an initial small pilot test of the messaging, all remaining eligible members will be messaged at the same time. The pilot will be deployed to about 500 eligible members and will only include the message arm and the small incentive arm.

For this recruitment study, there is no explicit consent process for study participants. Only those health system members who have not opted out of communications from CCRMC will be messaged. By design, 1/3 of eligible members will be offered \$25 for enrolling in the APT Webstudy and 1/3 will be entered into a drawing for a \$2500 prize. Importantly, any patient who chooses to enroll in the APT Webstudy will be consented in that study directly during the registration and enrollment process.

## 5. Methods

All CCRMC patients who meet the inclusion criteria will receive the same basic email or SMS message, inviting them to participate in the APT Webstudy. Eligible CCRMC patients will be allocated 1:1:1 to 3 study arms. The first arm, the messaging only arm, will just receive the invite message. The 2nd arm will receive, along with the invite, the offer of a \$25 gift card for completing enrollment into the APT Webstudy. The 3rd arm will receive, along with the invite, an offer of entry into a \$2500 prize drawing for completing enrollment into the APT Webstudy. The prize opportunity will be designed to allow participants to have a 1 in 100 chance of winning a \$2500 prize, thus the prize opportunity has the same expected value per enrollee as the certain \$25 incentive. Registration for and enrollment in the APT Webstudy includes web-based capture of demographic, medical, lifestyle and risk factors, as well as longitudinal web-based cognitive testing and symptom questionnaires. One cognitive assessment, the Cogstate Brief Battery, is a cognitive performance test; the other, the Cognitive Function Index (CFI), is a series of 15 questions probing subjective concerns related to cognitive performance. Participants will qualify as enrolled in the APT Webstudy if they complete the registration process as well as at least one of the two cognitive assessments. None of the data captured in the APT Webstudy data will be shared with the research team.

Two messages will be sent out to all eligible CCRMC patients, an initial invitation and a follow-up reminder will be sent approximately 2-weeks later. Invitations will be made via SMS or e-mail, depending on members' previously indicated mode of communication with the health system.

The intervention will be implemented by our collaborating partner, Contra Costa Health Services (CCHS), which runs Contra Costa Regional Medical Center (CCRMC) The trial team will track returned/invalid email or phone numbers as well as requests to opt out of communications at the participant level.

[figure not shown]
Randomization will be developed by the trial statistical team and shared with CCHS for implementation. Randomization will be stratified by age group (50-64, 65 and over), race/ethnic status (Latino/Hispanic, non-Hispanic White, non-Hispanic Black, non-Hispanic Asian, Other) and message modality (email or text) and will use a 1:1:1 allocation ratio across the three intervention arms. This is a single-blind study; only the intervention team and the statistical team will be unblinded to the intervention.

Primary Endpoint: APT Webstudy enrollment rate based on completion of at least one of the two APT Webstudy cognitive assessments (Cognitive Function Instrument [CFI] and/or Cogstate Brief Battery).

Enrollment will be captured by the APT Webstudy team, which is housed at ATRI, and will be shared with this study using the unique, anonymous code provided by CCRMC.

Secondary Endpoints: 1) Cost per enrollee and 2) Enrollees' rate of completion of both APT Webstudy cognitive assessments (CFI and Cogstate Brief Battery). Cost data are based on incentive payment costs while completion rate of both cognitive assessments will come from the APT Webstudy team and will be shared along with the unique, anonymous code provided by CCRMC.

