**Flow Diagram**

## **a. Data and Hypotheses**

Our final dataset will include the full sample of people we attempted to message, i.e., the anonymous dataset that we used for randomization along with the outcome measures from ATRI on APT Webstudy enrollment, incentive payments, and completion of both cognitive assessments.

Below we provide our main null hypotheses:

Aim 1, Primary Endpoint: Enrollment Rates

H1null: Financial incentives, certain small financial incentive or a prize opportunity incentive, will result in similar enrollment rates of CCRMC patients into the APT Webstudy relative to a message-only arm (active control).

Aim 2, H2null: A prize opportunity incentive will result in similar enrollment rate of CCRMC patients into the APT Webstudy as a certain small financial incentive with the same expected value.

- Secondary Endpoint(s): Cost per enrollee

H2null: The cost per APT Webstudy enrollee will be similar for the financial incentive arms compared with the message-only arm.

- Secondary Endpoint(s): Completion rates for both cognitive assessments

H3null: Completion rates for both cognitive assessments will be similar for the financial incentive arms compared with the message-only arm.

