### **c. Statistical Analysis**

The primary analysis will be based on the intention-to-treat (ITT) population of all messaged patients who are empaneled at Contra Costa Regional Medical Center (CCRMC), who are ages 50 and older and have no prior documentation of dementia.

Participant demographics and characteristics at time of messaging will be summarized for each intervention arm, using frequencies and percentages for categorical variables, and using mean, standard deviation, and quartiles for continuous variables. Comparisons across the three intervention groups will be done using a Chi-square test for categorical variables and an analysis of variance (ANOVA) test for continuous variables with Fisher's Exact Test or Dunnett's post-hoc tests, for categorical and continuous data respectively, to compare each active intervention arm against the control arm.

Our primary outcome is the enrollment status at 2-weeks. A multivariable logistic regression analysis will be performed to study the association between enrollment status and intervention arms (financial incentive arms vs active control arm) adjusting for age group (50-64, 65 and over), race and ethnic status (Latino/Hispanic, non-Hispanic White, non-Hispanic Black, non-Hispanic Asian, Other) and message modality (email or text). Separate analyses will be conducted for each financial incentive intervention arm against the active control arm.

All results will be reported as point estimates (e.g., percentage difference between groups) and interval estimates (two-sided 95% confidence intervals). All hypothesis tests to test group differences between each of the active intervention arms and the active control arm will be conducted at a two-sided alpha level of 0.025.

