Our secondary outcomes are cost per enrollee and completion of both cognitive assessments in the APT Webstudy. A multivariable linear regression will be performed to study the association between the cost per enrollee and intervention arms (financial incentive arm, active control arm) adjusting for age group (50-64, 65 and over), race and ethnic status (Latino/Hispanic, non-Hispanic White, non-Hispanic Black, non-Hispanic Asian, Other) and message modality (email or text). The other secondary outcome, completion of both cognitive assessments in the APT Webstudy, will be analyzed using a multivariable logistic regression analogous to the analysis of the primary outcome. Analyses of the secondary outcomes will also be conducted at a two-sided alpha level of 0.025, without further adjustment for multiplicity.

Prespecified sub-group analyses based on age group (50-64, 65 and over), race/ethnicity (Latino/Hispanic, non-Hispanic White, non-Hispanic Black, non-Hispanic Asian, Other) and message modality (email or text) will be conducted on all primary and secondary outcomes using analogous methods to the overall analysis. In addition, if feasible with available sample size, we will analyze sub-groups at the intersection of two or more of the identities of interest, e.g., racial/ethnic groups by age-group.

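### The test of completing both assessments is defined among enrollees, a group the incentive itself creates after randomization, while other passages can be read as counting everyone messaged

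*Protocol*

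**What the plan says.** - **Endpoint.** Section 5 (Methods) of the Protocol gives the only explicit denominator: "Enrollees' rate of completion of both APT Webstudy cognitive assessments".
- **Who is an enrollee.** The same section counts people as enrolled "if they complete the registration process as well as at least one of the two cognitive assessments". The $25 gift card or the prize entry is earned by enrolling, and enrollment is the primary endpoint.
- **Objective.** Section 2 names no denominator: "To assess the impact of financial incentives on cost per enrollee and, separately, completion of two cognitive assessments".
- **Dataset and hypothesis.** Section 5a says "Our final dataset will include the full sample of people we attempted to message" and lists completion of both assessments among the outcomes held in it. H3 reads "Completion rates for both cognitive assessments will be similar for the financial incentive arms compared with the message-only arm", again without a denominator.
- **Analysis.** Section 5c says this outcome "will be analyzed using a multivariable logistic regression analogous to the analysis of the primary outcome", at a two-sided level of 0.025.
- **Population.** Section 5c also says "The primary analysis will be based on the intention-to-treat (ITT) population of all messaged patients". That sentence covers the primary analysis only.

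**The concern.** Randomization makes the arms comparable among everyone messaged. It does not make them comparable among those who went on to enroll. If the incentive works, the incentive arm's enrollees include people with no counterpart among the control enrollees. A difference in their completion rate then mixes any effect on behavior with a change in who is counted. Adjusting for age group, race/ethnicity and message modality does not remove differences in motivation.

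The objective speaks of the impact of incentives, so H3 will be read causally. The endpoint definition leads to the enrollee comparison, whereas the reference to the primary analysis can be taken to mean all messaged patients. The two can lead to different decisions on H3 from the same data, and an analyst who has seen the data could choose between them.

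**Working it through.** **Inputs from the Protocol (sections 5b and 5c).** 16,000 per arm; enrollment 2% (control) and 2.59% (detectable incentive rate); two-sided alpha 0.025; stated power 90%.

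**Step 1: reproduce the stated power.** With p̄ = (0.02 + 0.0259)/2 = 0.02295:
- null SE = √(2 × 0.02295 × 0.97705 / 16,000) = 0.001674
- alternative SE = √((0.02 × 0.98 + 0.0259 × 0.9741) / 16,000) = 0.001674
- power = Φ[(0.0059 − 2.2414 × 0.001674) / 0.001674] = 0.900

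The 90% reproduces, so the enrollment rates can be used as they stand.

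**Step 2: size of the enrollee group.** Control: 0.02 × 16,000 = 320. Incentive: 0.0259 × 16,000 = 414.4. Extra: 94.4, and 94.4/414.4 = 22.8%.

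**Step 3: compare the two denominators.** Let *b* be the share completing both among people who would enroll without an incentive, taken as the same in both arms. Let *c* be the share among the extra enrollees. Both are assumptions, because the Protocol gives neither.

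- Expected completers: x₀ = 320*b* (control) and x₁ = 320*b* + 94.4*c* (incentive).
- Each comparison uses z = (p₁ − p₀) / √(p̄(1 − p̄)(1/n₀ + 1/n₁)), unadjusted, without continuity correction and evaluated at the expected counts.
- Denominators are 320 and 414.4 (enrollees), or 16,000 and 16,000 (all messaged).

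Example, *b* = 0.7 and *c* = 0.3: x₀ = 224 and x₁ = 224 + 28.32 = 252.32.
- Enrollees: 0.700 against 0.609, SE 0.0355, z = −2.56, p = 0.010.
- All messaged: 0.01400 against 0.01577, SE 0.00135, z = 1.31, p = 0.19.

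| b | c | x₀ | x₁ | Enrollees | p | All messaged | p |
|---|---|---|---|---|---|---|---|
| 70% | 70% | 224 | 290.1 | 70.0% vs 70.0% | 1.00 | 1.40% vs 1.81% | 0.003 |
| 70% | 60% | 224 | 280.6 | 70.0% vs 67.7% | 0.51 | 1.40% vs 1.75% | 0.011 |
| 70% | 50% | 224 | 271.2 | 70.0% vs 65.4% | 0.19 | 1.40% vs 1.70% | 0.033 |
| 70% | 40% | 224 | 261.8 | 70.0% vs 63.2% | 0.052 | 1.40% vs 1.64% | 0.084 |
| 70% | 30% | 224 | 252.3 | 70.0% vs 60.9% | 0.010 | 1.40% vs 1.58% | 0.19 |
| 90% | 60% | 288 | 344.6 | 90.0% vs 83.2% | 0.008 | 1.80% vs 2.15% | 0.023 |

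**Step 4: where each test crosses 0.025.** Solving the same formula for *c*:

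| b | Enrollee test against the incentive if c is at or below | All-messaged test for the incentive if c is at or above |
|---|---|---|
| 50% | 14% | 45% |
| 60% | 24% | 49% |
| 70% | 35% | 53% |
| 80% | 49% | 56% |
| 90% | 65% | 59% |

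From *b* = 50% to 80%, values of *c* between the two thresholds leave neither test significant in the direction shown. Of the rows tabulated, only *b* = 90% has an overlap (about 59% to 65%), where both are significant in opposite directions.

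**Step 5: false rejection of H3 among enrollees.** At *b* = 70% and *c* = 40%, the incentive changes nothing for those who would enroll anyway. Even so, the enrollee test rejects in about 38% of trials at a nominal 2.5%. It rejects at 2.5% only when *c* equals *b*.

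**The case against.** Several points can be made for the plan as it stands.

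- **There is silence, not contradiction.** Only the endpoint definition states a denominator. The objective and H3 state none, the dataset sentence describes contents, and the reference to the primary analysis may mean only the same model and covariates. A SAP could settle the population. This stands in part: no second denominator is written down. But the one that is written is the problem, and a SAP that used all messaged patients would contradict the Protocol's endpoint definition. On either reading some wording must change.
- **The enrollee rate is useful.** A registry wants to know whether people recruited with an incentive complete as much as others. This stands, and is a reason to keep the rate as a description. It does not support a test of the incentive's effect.
- **The all-messaged endpoint overlaps with the primary.** Completers of both are a subset of enrollees, and in the 70%/70% case the whole gain comes from enrollment. This is true and has to be accepted; showing the enrollee rate alongside keeps the missing information in view.
- **The size depends on assumptions.** This also stands. At *b* = 70%, rates of 50% and 40% among the extra enrollees give the same decision under both denominators. Opposite significant results are a corner case. The 2.59% is a detectable rate, not a forecast. That extra enrollees would complete less often is an inference from the rule that one assessment earns the incentive, not a finding from data.

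**Conclusion.** The concern holds. The only denominator fixed for this endpoint is formed after randomization by the outcome the incentive is meant to change, so the H3 test on it is not protected by randomization. Other passages allow a different estimand for the same test.

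At the design enrollment rates, about 23% of incentive-arm enrollees would be there because of the incentive. The H3 decision can then depend on the denominator even when all enrollees complete at the same rate (p = 1.00 against 0.003 at an assumed 70%). A significant result against the incentive needs a marked drop among the extra enrollees, to about 35% or below when the others complete at 70%.

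These figures rest on assumed completion rates, on no change among those who would enroll anyway, and on unadjusted tests at expected counts. The enrollee comparison would be sound if the incentive did not change who enrolls, but the trial is powered on its raising enrollment. One secondary endpoint is affected and the primary conclusion is not. It should be corrected before outcome data are seen by arm.

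**What to change.** Change the wording in three places of the Protocol: the secondary endpoint in section 5 (Methods), H3 in section 5a, and the secondary analysis in section 5c.

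- Define the tested endpoint as completion of both assessments (yes/no) among all messaged patients, with non-enrollees counted as not completing, analyzed with the primary logistic model.
- Report the completion rate among enrollees by arm descriptively, labeled as a non-randomized comparison and shown beside the enrollment result.

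No new data are needed, because section 5a already plans this outcome in the full messaged dataset. The price is a tested endpoint that partly repeats the primary one; the descriptive rate keeps the information on how fully enrollees complete.
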